### 14.3.6.2 Biochemistry

Table 14.3.6.2.1 Albumin at each assessment

	Deferiprone		Placebo		P-value (t-test)
	N	Mean $\pm$ SD (Min, Max)	N	Mean $\pm$ SD (Min, Max)	
Baseline	xx	xx.x $\pm$ xx.x (xx.x,xx.x)	xx	xx.x $\pm$ xx.x (xx.x,xx.x)	0xxxx
Month 1	xx	xx.x $\pm$ xx.x (xx.x,xx.x)	xx	xx.x $\pm$ xx.x (xx.x,xx.x)	0xxxx
Month 3	xx	xx.x $\pm$ xx.x (xx.x,xx.x)	xx	xx.x $\pm$ xx.x (xx.x,xx.x)	0xxxx
Month 6	xx	xx.x $\pm$ xx.x (xx.x,xx.x)	xx	xx.x $\pm$ xx.x (xx.x,xx.x)	0xxxx
Month 9	xx	xx.x $\pm$ xx.x (xx.x,xx.x)	xx	xx.x $\pm$ xx.x (xx.x,xx.x)	0xxxx
Month 12	xx	xx.x $\pm$ xx.x (xx.x,xx.x)	xx	xx.x $\pm$ xx.x (xx.x,xx.x)	0xxxx

Data source: 16.2.8.4 Listing of biochemistry

Note: Similar tables will be produced for total protein, GGT, glucose, bilirubin (total, direct, and indirect), AST, ALT, blood urea nitrogen, calcium, creatinine, total iron binding capacity, serum iron, and zinc.

Table 14.3.6.2.2 Change in albumin from baseline to at each follow-up assessment

	Deferiprone		Placebo		
	N	Mean ± SD (Min, Max)	N	Mean ± SD (Min, Max)	P-value (T-test)
Month 1	xx	xx.x ± xx.x (xx.x,xx.x)	xx	xx.x ± xx.x (xx.x,xx.x)	0.xxxx
Month 3	xx	xx.x ± xx.x (xx.x,xx.x)	xx	xx.x ± xx.x (xx.x,xx.x)	0.xxxx
Month 6	xx	xx.x ± xx.x (xx.x,xx.x)	xx	xx.x ± xx.x (xx.x,xx.x)	0.xxxx
Month 9	xx	xx.x ± xx.x (xx.x,xx.x)	xx	xx.x ± xx.x (xx.x,xx.x)	0.xxxx
Month 12	xx	xx.x ± xx.x (xx.x,xx.x)	xx	xx.x ± xx.x (xx.x,xx.x)	0.xxxx

Data source: 16.2.8.4 Listing of biochemistry

Note: Similar tables will be produced for total protein, GGT, glucose, bilirubin (total, direct, and indirect), AST, ALT, blood urea nitrogen, calcium, creatinine, total iron binding capacity, serum iron, and zinc.

Table 14.3.6.2.3 Shift table for albumin at baseline vs last assessment: deferiprone group

		Baseline			P-value (McNemar-Bowker's test)
	N (%)	Low	Normal	High	
Last assessment	Low	xx (xx)	xx (xx)	xx (xx)	0.xxxx
	Normal	xx (xx)	xx (xx)	xx (xx)	
	High	xx (xx)	xx (xx)	xx (xx)	

Data source: 16.2.8.4 Listing of biochemistry

Note: Similar tables will be produced for total protein, GGT, glucose, bilirubin (total, direct, and indirect), AST, ALT, blood urea nitrogen, calcium, creatinine, total iron binding capacity, serum iron, and zinc.

Table 14.3.6.2.4 Shift table for albumin at baseline vs last assessment: placebo group

		Baseline			P-value (McNemar-Bowker's test)
	N (%)	Low	Normal	High	
Last assessment	Low	xx (xx)	xx (xx)	xx (xx)	0.xxxx
	Normal	xx (xx)	xx (xx)	xx (xx)	
	High	xx (xx)	xx (xx)	xx (xx)	

Data source: 16.2.8.4 Listing of biochemistry

Note: Similar tables will be produced for total protein, GGT, glucose, bilirubin (total, direct, and indirect), AST, ALT, blood urea nitrogen, calcium, creatinine, total iron binding capacity, serum iron, and zinc.

Table 14.2.6.2.5 Percent of patients who had ALT > 2 x ULN, 3 x ULN, or 5 x ULN during the study

	Deferiprone	Placebo	P-value (Fisher's exact test)
ALT > 2 x ULN	xx% (xx / xx)	xx% (xx / xx)	0xxxx
ALT > 3 x ULN	xx% (xx / xx)	xx% (xx / xx)	0xxxx
ALT > 5 x ULN	xx% (xx / xx)	xx% (xx / xx)	0xxxx

Table 14.2.6.2.6 Percent of patients who had AST > 2 x ULN, 3 x ULN, or 5 x ULN during the study

	Deferiprone	Placebo	P-value (Fisher's exact test)
AST > 2 x ULN	xx% (xx / xx)	xx% (xx / xx)	0xxxx
AST > 3 x ULN	xx% (xx / xx)	xx% (xx / xx)	0xxxx
AST > 5 x ULN	xx% (xx / xx)	xx% (xx / xx)	0xxxx

### 14.3.7 Prolactin

Table 14.3.7.1 Prolactin at each assessment

	Deferiprone		Placebo		P-value (t-test)
	N	Mean $\pm$ SD (Min, Max)	N	Mean $\pm$ SD (Min, Max)	
Pre-dose	xx	xx.x $\pm$ xx.x (xx.x,xx.x)	xx	xx.x $\pm$ xx.x (xx.x,xx.x)	0xxxx
Post-dose	xx	xx.x $\pm$ xx.x (xx.x,xx.x)	xx	xx.x $\pm$ xx.x (xx.x,xx.x)	0xxxx
Month 12	xx	xx.x $\pm$ xx.x (xx.x,xx.x)	xx	xx.x $\pm$ xx.x (xx.x,xx.x)	0xxxx

Data source: 16.2.8.5 Listing of prolactin

Table 14.3.7.2 Change in prolactin from pre-dose to Month 12

	Deferiprone		Placebo		P-value (t-test)
	N	Mean $\pm$ SD (Min, Max)	N	Mean $\pm$ SD (Min, Max)	
Month 12	xx	xx.x $\pm$ xx.x (xx.x,xx.x)	xx	xx.x $\pm$ xx.x (xx.x,xx.x)	0xxxx

Data source: 16.2.8.5 Listing of prolactin

Table 14.3.7.3 LS Means for change in prolactin from pre-dose to Month 12 from ANCOVA model

	Deferiprone	Placebo	Deferiprone Minus Placebo	95% C.I.
N	xx	xx	xx	
	LS Mean $\pm$ SE	LS Mean $\pm$ SE	LS Mean $\pm$ SE	
Month 12	xxxx $\pm$ xxxx	xxxx $\pm$ xxxx	xxxx $\pm$ xxxx	(xxxx, xxxx)

Data source: 16.2.8.5 Listing of prolactin

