## 4 STUDY POPULATION

### 4.1 Number of Patients

A planned total of 64 patients will be enrolled in the study, 32 in each arm.

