**Notes:**

- Since SF level may be impacted by the presence of infection, it must additionally be verified that the child has had no signs of infection in the previous 7 days, including the day of the visit, and that the level of CRP is no greater than 20% higher than the normal range for the patient's age. . . If there are signs of infection and/or the CRP level is above this threshold, an SF level  $\geq 1000 \mu\text{g/L}$  must be checked again a minimum of a week later. (If an investigator has valid reason to believe that an SF level  $\geq 1000 \mu\text{g/L}$  may be attributable to infection even if this is not indicated by the CRP result, SF may be rechecked once more a minimum of one week later.)
- If a transfusion is scheduled on the day of the visit, the blood samples for serum ferritin, LPI, and TSAT must be collected before the transfusion is performed.
- Collect a urine specimen for urinalysis
- Perform a physical examination (to be completed by the investigator or a qualified delegate)
- Measure vital signs (heart rate, blood pressure, and body temperature)
- Measure weight and height/length
- Review and update transfusion history
- Ask about any adverse events that have occurred and concomitant medications that have been taken since the last site visit
- Additionally review the diary card for information on adverse events and use of concomitant medications, and file the diary card with the source documents
- Collect study medication containers, and check them to calculate treatment compliance
- Administer the final dose of study medication, ensuring that this is done at approximately the same time as at baseline, and note the exact time at which it is given
- Collect a blood sample for the assessment of prolactin at 1.5 hours ( $\pm 5 \text{ min}$ ) post-dose

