### 9.2 Determination of Sample Size and Study Power

The sample size for this study is 64 patients, randomized in a 1:1 ratio to the two arms. With this number of patients, there will be over 90% power to detect a statistically significant difference ( $\alpha = 0.05$ ) between the two treatment groups in the percentage of patients who have a serum ferritin level  $< 1000 \mu\text{g/L}$  at Month 12 if the deferiprone arm and the placebo arm have an expected incidence of 70% and 20%, respectively.

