**V: Verify**

-  Visits are scheduled every 30 days ( $\pm$  10 days).
-  Patients terminate from the study at Month 12 or when they have been found to have a serum ferritin level  $\geq$  1000  $\mu$ g/L at 2 consecutive visits, whichever comes first.
-  Hematology: Hemoglobin, total WBC count, ANC, MCV, and platelet count.
-  Blood chemistry: Total protein, GGT, glucose, bilirubin (total, direct, and indirect), AST, ALT, albumin, blood urea nitrogen, calcium, creatinine, total iron binding capacity, serum iron, zinc, and CRP.
-  The results obtained at screening for blood chemistry, physical examination, and urinalysis are considered to be the baseline results. These tests are not repeated at Day 0.
-  A blood sample for DNA testing is to be taken only if DNA confirmation of a diagnosis of beta-thalassemia is not available at the time of screening.
-  Urinalysis: pH, specific gravity, glucose, protein, ketones, blood, and (if indicated by the dipstick results), sediment microscopy. If there is blood in the urine or three or more “plus signs” for protein, samples must be sent for microscopy.
-  Hepatitis B, hepatitis C, and HIV.
-  Heart rate, blood pressure, and body temperature. At the time of these measurements, the child must be calm and not crying.
-  For infants not yet able to stand upright, stature is measured as recumbent length.
-  For TSAT and SF, the values obtained at the screening visit (not those obtained at baseline) are used for the eligibility criteria.
-  Blood samples for the assessment of prolactin are taken pre-dose and at  $+ 1.5$  h  $\pm$  5 minutes post-dose. The second set of samples are taken only from patients who are still in the study at Month 12; they are not taken from patients who are terminated before that time.
-  Dosing: Deferiprone oral solution 80 mg/mL or matching placebo solution.

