## **5. Statistical Analysis**

A two-sided p-value of 0.05 will be used as the significance level for the determination of statistical significance in all statistical tests.

All statistical analyses of efficacy and safety data will be performed using SAS (version 9.4 or higher) on the Windows operating system.

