## 5.7 Analysis of Safety

Descriptive statistics (mean, standard deviation, minimum, and maximum) will be produced for continuous variables, and frequency tables will be produced for discrete variables by treatment group. Summaries of adverse events and serious adverse events will be produced by treatment group. Shift tables will be generated for comparing the screening/baseline values and end of study values of the relevant measures.

The following safety data will be summarized by treatment group:

- Adverse events (AEs), adverse drug reactions (ADRs), serious adverse events (SAEs), and serious adverse drug reactions (SADRs)
- Number of discontinuations due to AEs
- Hematology assessments
- Biochemistry assessments
- Urinalysis
- Vital signs
- Prior and concomitant medications

Prolactin is measured at baseline and Month 12. The change in prolactin level from baseline to Month 12 will be compared between the two treatment groups using an ANCOVA model with baseline value as a covariate and treatment as the main factor.

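### The Day 0 post-dose prolactin comparison uses an unadjusted t-test although each child's own pre-dose value is available; an ANCOVA on that value is more precise at no cost in samples, and the Month 12 row needs a label

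*SAP*

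**What the plan says.** **Sampling.** SAP Table 1, footnote 12, repeats the rule in Protocol Table 5.1: "Blood samples for the assessment of prolactin are taken pre-dose and at" 1.5 h after the dose, within 5 minutes. The second set is taken only from children still in the study at Month 12. Protocol section 5.1 lists a pre-dose sample at both the Baseline and the Month 12 visit and, after the dose given on site, instructs staff at each: "Collect a blood sample for the assessment of prolactin at 1.5 hours". The early termination visit does not include prolactin.

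**Endpoint and model.** The listed safety endpoint is the change in prolactin from baseline to Month 12 (Protocol 9.1.3, SAP 5.3). SAP 5.7 says: "The change in prolactin level from baseline to Month 12 will be compared between the two treatment groups using an ANCOVA model", with the baseline value as covariate. Neither place says whether the pre-dose or the post-dose sample is meant.

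**Shells (SAP 14.3.7).**
- Table 14.3.7.1 gives levels in three rows (Pre-dose, Post-dose, Month 12), each with a t-test p-value.
- Table 14.3.7.2 gives the change from pre-dose to Month 12, with a t-test.
- The third table is "Table 14.3.7.3 LS Means for change in prolactin from pre-dose to Month 12 from ANCOVA model".

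No shell relates a post-dose value to the same child's pre-dose value at that visit.

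**The concern.** The Day 0 pair is the prolactin comparison with the fullest data. Every dosed child is due to give both samples, before anyone can leave the study. The Month 12 set comes only from children who remain, and leaving depends partly on ferritin, which treatment is meant to change. Yet the Day 0 post-dose value gets only an unadjusted comparison of levels, which leaves between-child variation in prolactin in the error term although the pre-dose sample could remove part of it.

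There is also a labelling gap. Two prolactin samples are due at Month 12, but the shells have one Month 12 row with no pre-dose or post-dose label. The SAP text does not say which sample enters the change, and no row names the other.

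At stake are the precision of one safety comparison and the clear definition of one safety endpoint.

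**Working it through.** **1. The plan's own figures.** The documents give no SD, correlation, target difference or power for prolactin, so there is no prolactin figure to reproduce. The only stated power is for the primary ferritin comparison: "there will be over 90% power to detect a statistically significant difference" if the arms "have an expected incidence of 70% and 20%, respectively". With 32 per arm and two-sided 0.05, this comes to 99.1% by the pooled z formula and 98.3% by exact enumeration of Fisher's test. The statement is true and nothing below alters it.

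**2. Samples against shell rows.** The protocol has 2 visits × 2 samples = 4 prolactin time points for a child who reaches Month 12, and 2 for a child who leaves earlier. Table 14.3.7.1 has 3 rows, so one Month 12 sample has no row of its own.

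**3. Inputs for the Day 0 comparison.**
- n = 32 per arm (Protocol 4.1: "A planned total of 64 patients will be enrolled in the study, 32 in each arm"), assuming essentially all give both Day 0 samples.
- Two-sided α = 0.05 (SAP 5: "A two-sided p-value of 0.05 will be used as the significance level").
- ρ, the correlation between the Day 0 pre-dose and post-dose values, is assumed: 0.3, 0.5, 0.7.

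**4. Variance.** With residual SD σ for the post-dose level:
- t-test: variance of the arm difference = 2σ²/n.
- ANCOVA on the pre-dose value: about (2σ²/n)(1 − ρ²).
- Ratio = 1 − ρ²: 1 − 0.09 = 0.91; 1 − 0.25 = 0.75; 1 − 0.49 = 0.51.

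**5. What that buys.** The noncentral t distribution with 64 − 2 = 62 degrees of freedom gives a detectable standardized difference at 80% power of 0.71 for the t-test. For ANCOVA this is multiplied by √(1 − ρ²).

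| Assumed ρ | Variance ratio | Detectable difference (SD units) | Power at 0.7 SD |
|---|---|---|---|
| t-test | 1 | 0.71 | 79% |
| 0.3 | 0.91 | 0.68 | 82% |
| 0.5 | 0.75 | 0.62 | 89% |
| 0.7 | 0.51 | 0.51 | 97% |

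ANCOVA has 61 rather than 62 degrees of freedom. Using 61 leaves the detectable differences unchanged to two decimals. At ρ = 0.5 the gain equals that of enlarging each arm from 32 to 32/0.75, about 43 children.

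**6. Which Month 12 sample is meant.** Tables 14.3.7.2 and 14.3.7.3 start from pre-dose. The Baseline Visit notes in Protocol 5.1 describe Month 12 prolactin as drawn about 12 hours after the last dose and before the next. Together these imply pre-dose to pre-dose, though neither SAP 5.7 nor the shells say so.

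**The case against.** **The t-test is valid and the acute response is not an endpoint.** Both are true. Randomisation protects a comparison of post-dose levels, and unadjusted t-tests appear throughout the descriptive shells. The listed endpoint already has a baseline-adjusted ANCOVA. So the Day 0 ANCOVA improves a p-value that the SAP already plans to report, and it should be labelled supportive.

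**Shell layouts are not binding.** The SAP says that tables may differ from the shells, and a prolactin listing (16.2.8.5) is planned. This weakens the labelling point. The Month 12 post-dose sample is not lost; no table row names it. The Post-dose row also carries no visit label, so reading it as Day 0 is an inference.

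**The gain rests on an assumed correlation.** It does. At a correlation near zero the adjustment brings nothing and costs one degree of freedom.

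**Stronger readings that a reader might infer, which the documents do not support:**
- *That the plan pools or averages the two Month 12 samples.* Nothing says so, and the protocol timing note points to the pre-dose sample.
- *That every child gives four samples.* Only those still in the study at Month 12 do.
- *That Month 12 prolactin will come from about 22 and 6 children* (32 × 0.70 = 22.4; 32 × 0.20 = 6.4). Those rates are for ferritin below 1000 µg/L, not attendance. Ferritin exit needs two consecutive high values, so a child first above the threshold at Month 11 still attends Month 12; other withdrawals act the other way.
- *That Month 12 should have the same ANCOVA as Day 0.* Its covariate would be measured after treatment and in a selected subset, so randomisation would not protect the contrast. The Day 0 post-dose sample also follows the first dose at the starting step, and the Month 12 one a dose at a later step, so they do not reflect the same exposure.

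**Conclusion.** The point holds as a free gain in precision together with a clarification. The planned t-test on the Day 0 post-dose row is correct but less precise than the data allow. Adjusting for the Day 0 pre-dose value would remove about 9%, 25% or 49% of the variance of the arm difference at ρ = 0.3, 0.5 or 0.7.

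This rests on three assumptions: the Post-dose row is Day 0, essentially all 64 children give both Day 0 samples, and ρ lies in the range shown.

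The unlabelled Month 12 row is missing detail. The intended comparison can be inferred from the protocol, but the SAP should state it. A reader should not conclude that the prolactin endpoint lacks an adjusted analysis or that the planned test is biased.

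**What to change.** 1. In Table 14.3.7.1, label the Pre-dose and Post-dose rows as Day 0. Replace the t-test on the Day 0 post-dose row with an ANCOVA of that value on treatment, with the Day 0 pre-dose value as covariate. Report the adjusted difference with a 95% confidence interval, and label it supportive because the acute response is not a listed endpoint.
2. Split the Month 12 row into pre-dose and 1.5 h post-dose. State in SAP 5.7 and in Tables 14.3.7.2 and 14.3.7.3 that the change is Month 12 pre-dose minus Day 0 pre-dose, with the Day 0 pre-dose value as the ANCOVA covariate.
3. Report the Month 12 post-dose value and its post-minus-pre change descriptively by arm, without a between-arm test, and note that the data come only from children still in the study.

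The cost is a few lines of SAP and shell text and one extra model, settled before unblinding. No sample, visit or sample-size change is needed. The supportive model replaces a planned p-value, so it adds no test.

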#### 14.4 Other analyses

Table 14.4.1 Compliance (%) at each assessment

	Deferiprone		Placebo		P-value (t-test)
	N	Mean ± SD (Min, Max)	N	Mean ± SD (Min, Max)	
Month 1	xx	xx ± xx (xx, xx)	xx	xx ± xx (xx, xx)	0xxxx
Month 2	xx	xx ± xx (xx, xx)	xx	xx ± xx (xx, xx)	0xxxx
Month 3	xx	xx ± xx (xx, xx)	xx	xx ± xx (xx, xx)	0xxxx
Month 4	xx	xx ± xx (xx, xx)	xx	xx ± xx (xx, xx)	0xxxx
Month 5	xx	xx ± xx (xx, xx)	xx	xx ± xx (xx, xx)	0xxxx
Month 6	xx	xx ± xx (xx, xx)	xx	xx ± xx (xx, xx)	0xxxx
Month 7	xx	xx ± xx (xx, xx)	xx	xx ± xx (xx, xx)	0xxxx
Month 8	xx	xx ± xx (xx, xx)	xx	xx ± xx (xx, xx)	0xxxx
Month 9	xx	xx ± xx (xx, xx)	xx	xx ± xx (xx, xx)	0xxxx
Month 10	xx	xx ± xx (xx, xx)	xx	xx ± xx (xx, xx)	0xxxx
Month 11	xx	xx ± xx (xx, xx)	xx	xx ± xx (xx, xx)	0xxxx
Month 12	xx	xx ± xx (xx, xx)	xx	xx ± xx (xx, xx)	0xxxx

Data source: 16.2.5.1 Listing of compliance

Table 14.4.2 Overall mean of transfusional iron input (mg/kg/day) during the study

	Deferiprone		Placebo		
	N	Mean ± SD (Min, Max)	N	Mean ± SD (Min, Max)	P-value (t-test)
Overall mean of transfusional iron input (mg/kg/day) during the study	xx	xx.x ± xx.x (xx.x, xx.x)	xx	xx.x ± xx.x (xx.x, xx.x)	0.xxxx

Data source: 16.2.9.7 Listing of transfusion

Table 14.4.3 Overall mean of total daily dose (mg/kg/day) during the study

	Deferiprone		Placebo		
	N	Mean ± SD (Min, Max)	N	Mean ± SD (Min, Max)	P-value (t-test)
Overall mean of total daily dose (mg/kg/day) during the study	xx	xx.x ± xx.x (xx.x, xx.x)	xx	xx.x ± xx.x (xx.x, xx.x)	0.xxxx

Data source: 16.2.9.8 Listing of exposure

Table 14.4.4 Patient exposure to study medication

	Deferiprone	Placebo
Total Patients Exposed [N]	xx	xx
Total Patient-Years Exposure	xxx	xxx
Length of Exposure (years)		
Mean	xx.x	xx.x
SD	xx.x	xx.x
Median	xx.x	xx.x
Min, Max	xx.x, xx.x	xx.x, xx.x

Data source: 16.2.9.8 Listing of exposure

Table 14.4.5 Duration of study drug exposure

	Deferiprone	Placebo
Duration of Exposure [n(%)]		
Any Exposure	xx (xx.x)	xx (xx.x)
>= 1 Month	xx (xx.x)	xx (xx.x)
>= 2 Months	xx (xx.x)	xx (xx.x)
>= 3 Months	xx (xx.x)	xx (xx.x)
>= 4 Months	xx (xx.x)	xx (xx.x)
>= 5 Months	xx (xx.x)	xx (xx.x)
>= 6 Months	xx (xx.x)	xx (xx.x)
>= 9 Months	xx (xx.x)	xx (xx.x)
>= 12 Months	xx (xx.x)	xx (xx.x)

Data source: 16.2.9.8 Listing of exposure
